10.4 Routine Adverse Event Reporting

All Adverse Events **must** be reported in routine study data submissions. **AEs reported expeditiously through CTEP-AERS must also be reported in routine study data submissions.**

Adverse event data collection and reporting, which are required as part of every clinical trial, are done to ensure the safety of patients enrolled in the studies as well as those who will enroll in

future studies using similar agents. AEs are reported in a routine manner at scheduled times during the trial using Medidata Rave. For this trial the Adverse Event CRF is used for routine AE reporting in Rave.

10.5 Pregnancy

Although not an adverse event in and of itself, pregnancy as well as its outcome must be documented via **CTEP-AERS**. In addition, the **Pregnancy Information Form** included within the NCI Guidelines for Adverse Event Reporting Requirements must be completed and submitted to CTEP. Any pregnancy occurring in a patient or patient's partner from the time of consent to 90 days after the last dose of study drug must be reported and then followed for outcome. Newborn infants should be followed until 30 days old. Please see the "NCI Guidelines for Investigators: Adverse Event Reporting Requirements for DCTD (CTEP and CIP) and DCP INDs and IDEs" (at http://ctep.cancer.gov/protocolDevelopment/adverse_effects.htm) for more details on how to report pregnancy and its outcome to CTEP.

10.6 Secondary Malignancy

A *secondary malignancy* is a cancer caused by treatment for a previous malignancy (e.g., treatment with investigational agent/intervention, radiation or chemotherapy). A secondary malignancy is not considered a metastasis of the initial neoplasm.

CTEP requires all secondary malignancies that occur following treatment with an agent under an NCI IND/IDE be reported expeditiously via CTEP-AERS. Three options are available to describe the event:

- Leukemia secondary to oncology chemotherapy (e.g., acute myelocytic leukemia [AML])
- Myelodysplastic syndrome (MDS)
- Treatment-related secondary malignancy

Any malignancy possibly related to cancer treatment (including AML/MDS) should also be reported via the routine reporting mechanisms outlined in each protocol.

10.7 Second Malignancy

A second malignancy is one unrelated to the treatment of a prior malignancy (and is **NOT** a metastasis from the initial malignancy). Second malignancies require **ONLY** routine AE reporting unless otherwise specified.

11. STUDY CALENDAR

Baseline evaluations are to be conducted within 1 week prior to start of protocol therapy. Scans and X-rays must be done \leq 4 weeks prior to the start of therapy. In the event that the patient's condition is deteriorating, laboratory evaluations should be repeated within 48 hours prior to

initiation of the next cycle of therapy.

NCI Protocol #: 10410
 Version Date: June 2, 2022

	Pre-Study	Wk 1	Wk 2	Wk 3	Wk 4	Wk 5	Wk 6	Wk 10 (4 wks following chemoRT) End of study for toxicity assessment	Wk 14-18 (8-12 wks following chemoRT) End of study for response assessment
IPdR		A	A	A	A	A	A		
Capecitabine		B	B	B	B	B	B		
Radiation therapy		C	C	C	C	C	C		
Surgical resection									X
mFOLFOX6 × 8 cycles	X								
Informed consent	X								
Demographics	X								
Medical history	X								
Concurrent meds	X	X	X	X	X	X	X	X	X
Physical exam	X	X	X	X	X	X	X	X	X
Vital signs	X	X	X	X	X	X	X	X	X
Height	X								
Weight	X	X	X	X	X	X	X	X	X
Performance status ^a	X	X				X		X	X
CBC w/diff, plts	X	X	X	X	X	X	X	X	X
Carcinoembryonic Antigen (CEA)	X							X	X
Comprehensive Chemistry Panel ^b	X	X	X	X	X	X	X	X	X
EKG (as indicated)	X								
Blood draws for PK and IUDR incorporation in granulocyte assays (mandatory)			X ^{c,d}	X ^{c,d}		X ^{c,d}			
Adverse event evaluation		X	X	X	X	X	X	X	
Radiologic evaluation	X								X ^e
Digital rectal exam and proctoscopic or sigmoidoscopic exam									X ^e
Pregnancy test ^f	X								

A: IPdR: Dose as assigned; PO QD administered throughout radiation (38 days, 6 weeks)
 B: Capecitabine: 825 mg/m² PO BID on days of radiation therapy (taken Monday morning through Friday evening each week of RT)
 C: Radiation therapy: 1.8 Gy/day × 28 doses (50.4 Gy total dose), M-F Days 1-5, 8-12, 15-19, 22-26, 29-33, 36-38
 a: Performance status evaluations are to be conducted every 4 weeks.
 b: Albumin, alkaline phosphatase, total bilirubin, bicarbonate, BUN, calcium, chloride, creatinine, glucose, LDH, magnesium, phosphorus, potassium, total protein, SGOT [AST], SGPT [ALT], sodium.
 c: 10 mL Blood for PK studies in sodium heparin tubes will be drawn on Day 8, prior to IPdR dose; and then after IPdR dose at 30 min, 60 min, 120 min and 240 min. On Day 21 and Day 35, blood will be drawn at 1-2 hours after the IPdR dose.
 d: 5 mL blood for measuring IUDR incorporation in granulocytes will be drawn in EDTA tubes prior to IPdR dose on Day 8, and at 1-2 hours after the IPdR dose on Day 21 and Day 35.
 e: Scans, digital rectal exam, and proctoscopic or sigmoidoscopic exam will be obtained at 6-10 weeks following completion of therapy (pre-operatively within 2 weeks of surgery)
 f: Pregnancy test for women of childbearing potential.

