6.2 Definition of Dose-Limiting Toxicity

Management and dose modifications associated with the above AEs are outlined in Section 7.

DLTs will be captured until 4 weeks after completion of IPdR therapy and will be graded according to the CTCAE v5.0. DLTs will be defined as clinically significant grade 3 or 4 toxicities possibly or probably related to study treatment.

- Grade 4 neutropenia (ANC < 500/mm³)
- Grade 4 electrolyte toxicities
- ANC <1000/mm³ with fever (temp >101 F) or infection
- Grade 4 thrombocytopenia: Platelets <25,000/mm³
- Platelets <50,000/mm³ requiring transfusion
- Grade 3 or 4 treatment related non-hematologic toxicities excluding alopecia.
- Patients who receive <67% of intended IPdR secondary to treatment related toxicities will also be considered as having a DLT

In addition, during chemoradiation, DLTs will also include AEs requiring interruptions of radiation for >5 consecutive scheduled fractions (and / or ≥ 9 total scheduled fractions) or for >10 consecutive scheduled doses of capecitabine (and / or ≥ 19 total scheduled doses of capecitabine). The following AEs will not be considered DLTs:

- Any grade of alopecia,
- Grade 3 arthralgia or myalgia,
- Brief (<1 week) grade 3 fatigue,
- Grade 3 fever,

- Grade 3 diarrhea or vomiting responding to supportive care
 - Grade 3 nausea, vomiting or diarrhea will be considered a DLT if it occurs for greater than 48 hours despite maximal medical support.
- Grade 3 radiation dermatitis,
- Grade 3 or 4 electrolyte abnormalities will not be considered DLTs if the electrolyte disorder can be corrected to grade 2 or less within 72 hours.

All patients who have received at least one dose of IPdR are evaluable for toxicities.

For dose escalation decisions, patients should have completed $\geq 80\%$ of the planned chemoradiation doses unless the reason for discontinuation is an AE that qualifies for DLT.

Dose escalation will proceed within each cohort in Part IB according to the following scheme. DLT is defined above.

Number of Patients with DLT at a Given Dose Level	Escalation Decision Rule
0 out of 3	Enter 3 patients at the next dose level.
≥ 2	Dose escalation will be stopped.

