6.8 Duration of Follow-Up

Patients will be followed for 4 weeks after completion of study treatment, removal from study, or until death, whichever occurs first. Patients will be assessed at 4 weeks (approximately 30 days) following completion of IPdR (Week 10 unless there were delays in therapy). This will be the final assessment for study-related toxicity. Patients will undergo surgical resection 8-12 weeks following completion of study treatment, and study-related response will be assessed at that time. Patients removed from study for unacceptable AE(s) will be followed until resolution or stabilization of the adverse event.

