10.3 Expedited Adverse Event Reporting

10.3.1 Rave-CTEP-AERS Integration

The Rave Cancer Therapy Evaluation Program Adverse Event Reporting System (CTEP-AERS) integration enables evaluation of Adverse Events (AEs) entered in Rave to determine whether they require expedited reporting and facilitates entry in CTEP-AERS for those AEs requiring expedited reporting. Sites must initiate all AEs for this study in Medidata Rave.

Include the following (highlighted) paragraphs about pre-treatment AEs only if the study requires reporting of pre-treatment AEs. Pre-existing medical conditions are not considered adverse events and therefore should not be reported on an Adverse Event form.

Pre-treatment AEs: AEs that occur after informed consent is signed and prior to start of treatment are collected in Medidata Rave using the Pre-treatment Adverse Event form.

Pre-existing medical conditions (formerly referred to as baseline AEs) identified during baseline assessment are not considered AEs and therefore should not be reported on the Pre-treatment Adverse Event form. If these pre-existing conditions worsen in severity, the investigator must reassess the event to determine if an expedited report is required. Whether or not an expedited report is required, the worsened event should be reported as a routine AE.

Treatment-emergent AEs: All AEs that occur after start of treatment are collected in Medidata Rave using the Adverse Event form, which is available for entry at each treatment course or reporting period and is used to collect AEs that start during the period or persist from the previous reporting period. AEs that occur 30 Days after the Last Administration of the Investigational Agent/Intervention are collected using the Late Adverse Event form.

Prior to sending AEs through the rules evaluation process, site staff should verify the following on the Adverse Event form in Rave:

- The reporting period (course/cycle) is correct, and
- AEs are recorded and complete (no missing fields) and the form is query-free.

The CRA reports AEs in Rave at the time the Investigator learns of the event. If the CRA modifies an AE, it must be re-submitted for rules evaluation.

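### No adverse-event evaluation is scheduled at the Week 14-18 visit, so non-serious events between Week 10 and surgery depend on unprompted reporting

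*Combined protocol and SAP*

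**What the plan says.** In the section 11 calendar, the Week 10 column is headed "End of study for toxicity assessment" and the Week 14-18 column "End of study for response assessment". The row "Adverse event evaluation" is marked at each of Weeks 1 to 6 and at Week 10, and is blank at Week 14-18. In that last column the row "CBC w/diff, plts" is marked. So are chemistry, CEA, physical exam, vital signs, weight, performance status and concurrent medications.

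The text agrees with the calendar. Section 6.8 states: "Patients will be followed for 4 weeks after completion of study treatment, removal from study, or until death, whichever occurs first". Of the visit four weeks after treatment it adds: "This will be the final assessment for study-related toxicity". The Schema and section 6.1.1 say the same. Section 6.2 closes the DLT window at that point: "DLTs will be captured until 4 weeks after completion of IPdR therapy". Section 6.6 places surgery 8 to 12 weeks after study treatment.

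Section 10.3.1 looks further ahead: "AEs that occur 30 Days after the Last Administration of the Investigational Agent/Intervention are collected using the Late Adverse Event form". It assigns no visit, end date or grade threshold to that form. Section 10.4 requires all adverse events to be included in routine data submissions.

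Primary objective 1.1.2 is to determine the CTCAE toxicities of IPdR, capecitabine and RT together. It sets no time limit.

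**The concern.** The plan provides a form for late events but no occasion on which it must be filled in. At Week 14-18 the site examines the patient, weighs the patient and repeats the safety labs, yet nothing scheduled asks staff to elicit symptoms or grade what they find. Sections 6.1.1 and 6.8 tell the same staff that toxicity assessment has already finished.

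Volunteered events are usually recorded less completely, and less evenly across sites and dose levels, than solicited ones. With cohorts of three to six patients per dose level, one or two unrecorded events can change the toxicity description at a dose. That description is a primary objective, and section 2.1.4 says the study will inform whether IPdR becomes an experimental arm of NRG-GI002. Exploratory objective 1.3.1, on RT exposure and adverse events, uses the same data.

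**Working it through.** This is a question about the visit schedule. It depends on no power or error-rate figure, so the check is calendar arithmetic followed by a comparison of sections.

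**Inputs.** Last RT fraction on Day 38, in Week 6 (section 11, footnote C). Toxicity visit 4 weeks later (section 6.8). Surgery 8 to 12 weeks after treatment (section 6.6). Late Adverse Event form from 30 days after the last administration (section 10.3.1).

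**Calendar, assuming no treatment delay.**
- Toxicity visit: Week 6 + 4 = Week 10; Day 38 + 28 = Day 66.
- Late form begins: Day 38 + 30 = Day 68.
- Surgery: Week 6 + 8 = Week 14 to Week 6 + 12 = Week 18; Day 38 + 56 = Day 94 to Day 38 + 84 = Day 122.
- Interval with no scheduled adverse-event evaluation before surgery: 94 - 66 = 28 days to 122 - 66 = 56 days, that is 4 to 8 weeks.
- Part of that interval in which the late form applies: 94 - 68 = 26 days to 122 - 68 = 54 days.

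The plan's own week numbers (10 and 14-18) reproduce.

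**What applies after Week 10.**

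| Source | Provision | Tied to a visit? |
|---|---|---|
| Section 11 | Adverse-event row blank at Week 14-18 | No |
| Schema, 6.1.1, 6.8 | Week 10 is the last toxicity assessment | Ends at Week 10 |
| 10.3.1 | Late Adverse Event form, any grade, seriousness or attribution | No |
| 10.4 | All events in routine submissions | No |
| 10.3.3, footnote 1 | Expedited reports of serious, related events after 30 days (Grade 3-5, or Grade 2 with hospitalization) | No |
| 6.8 | Patients removed for unacceptable events followed to resolution or stabilization | That subgroup only |

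Collection is therefore permitted, and under section 10.4 required, but it is never prompted. Section 6.8 ends general follow-up at four weeks, while section 10.3.1 presumes that events are still being recorded later. A site reading section 6.8 alone could reasonably stop asking.

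**Section 9.1 for context.** The chance that none of six patients shows a toxicity is (1 - p)^6. For p = 0.30, 0.7^6 = 0.1176 (stated as 0.117). For p = 0.50, 0.5^6 = 0.0156 (stated as 0.016). Both reproduce, apart from truncation of the first. They describe events that are recorded when they occur, and do not address events arising when nobody is asked to look.

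**The case against.** The strongest reply is that Week 10 is a deliberate and consistent choice. The Schema, sections 6.1.1 and 6.8 and the calendar all give it, and it coincides with the end of the DLT window. It also matches the preceding IPdR phase 1 trial described in section 2.2.1.3: 28 days of drug with assessment to Day 56, again four weeks after treatment. Nor is the later visit blind to toxicity, since its exam and labs would show many abnormalities and the Late Adverse Event form gives them somewhere to go.

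Much of this stands. It justifies the DLT window, which is not challenged here, and it confines the gap to active solicitation and grading at one visit. It does not explain why a form exists that no visit triggers, or why an objective without a time limit is served by scheduled evaluation that stops four weeks after treatment.

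Three stronger readings are tempting, and the documents do not support them.

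- *After Week 10 only serious, related events are collected.* The serious-and-related limit in section 10.3.3 governs expedited reports. Sections 10.3.1 and 10.4 cover all adverse events. Sections 10.5 to 10.7 add routes for pregnancy and for secondary and second malignancies.
- *The gap covers operative and healing events.* Surgery falls at Weeks 14-18, so the 4 to 8 weeks after Week 10 are pre-operative. Healing comes later, and the calendar has no post-operative visit.
- *The loss can be put in numbers.* The gap is 4/14 = 29% to 8/18 = 44% of the weeks from start of treatment to surgery, but that is a share of time, not of toxicity. Likewise 1 - 0.7^6 = 0.88 is the chance of seeing a 30% toxicity at least once in six patients, not the number missed. The documents give no late-onset rate from which to derive one.

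**Conclusion.** The point holds as a low-cost improvement to data collection. Adverse-event evaluation is unscheduled for 28 to 56 days before surgery, at the end of which every patient who proceeds as planned has a visit with exam and labs. Non-serious events in that interval rest on unprompted reporting, and section 6.8 reads as though no reporting is expected.

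The effect is on the completeness of the toxicity description under objective 1.1.2. The MTD rules, DLT counts, sample size and the section 9.1 probabilities are unchanged. The number of events at stake cannot be estimated from the documents. The interval assumes treatment finishes on Day 38; delays move all the dates together. That solicited capture is more complete than volunteered capture is general trial experience, not something the protocol states.

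**What to change.** 1. Mark the adverse-event row in the existing Week 14-18 column of the section 11 calendar.
2. State in section 6.8 that events from Week 10 to that visit are recorded on the Late Adverse Event form. Define the handover from the regular form, because Week 10 falls at 28 days and section 10.3.1 starts the late form at 30.
3. Reconcile the statements in the Schema, section 6.1.1 and section 6.8 that Week 10 is final with section 10.3.1. One way is to call Week 10 the final assessment for DLT and dose-escalation purposes.
4. Say up to what point events count at the Week 14-18 visit. Under calendar footnote e and section 12.1.1.1, the pre-operative exam may take place up to two weeks before surgery or immediately before it. State whether intra-operative events are included. Post-operative healing lies outside this change, since it would need a visit that the plan does not have.
5. In section 9, add that events after Week 10 will be summarised separately by dose level and will not enter the DLT count. Leave the DLT window in section 6.2 unchanged.

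The cost is about one additional form per patient, at most about 30 on the planned sample size, at a visit already scheduled, plus the data entry.

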12. MEASUREMENT OF EFFECT

Although the clinical benefit of this drug has not yet been established, the intent of offering this treatment is to provide a possible therapeutic benefit, and thus the patient will be carefully monitored for tumor response and symptom relief in addition to safety and tolerability.

12.1 Antitumor Effect – Solid Tumors

Disease response in this study will be measured by achievement of pathologic complete response at the time of surgical resection and determination of the NAR score. The NAR score requires determination of clinical complete response by digital rectal examination and either proctoscopic or sigmoidoscopic examination. Radiologic assessment of response is not used in this study, except to confirm that no metastatic disease has developed after chemoradiotherapy (assessment performed within 2 weeks of surgical resection).

12.1.1 Clinical Complete Response (CCR)

12.1.1.1 Timing of assessments

For the purposes of this study, patients must have a formal perioperative assessment documenting clinical response of the primary rectal tumor via digital rectal exam (DRE) *and* proctoscopic or sigmoidoscopic exam. DRE and proctoscopic or sigmoidoscopic exam may be done immediately before surgery.

12.1.1.2 Definition of CCR

No visible or palpable rectal tumor on direct examination. Nodes are not included in this definition.

12.1.2 Pathologic complete response (pCR)

In rectal cancer, the absence of viable tumor cells in the resection specimen (primary tumor mass, surrounding tissue and lymph nodes, T0 N0 M0) at the time of surgery, termed pathologic complete response (pCR) (Ryan *et al.*, 2005; Martin *et al.*, 2012). pCR determination will be made by the pathologist at the treating institution.

12.1.3 Neoadjuvant Rectal Score (NAR)

NAR is calculated based on the clinical T stage (cT), pathological T (pT) and pN stages as (Valentini *et al.*, 2011, George *et al.*, 2015):

$$\text{NAR} = [5\text{pN} - 3(\text{cT} - \text{pT}) + 12]^2 / 9.61$$

13. STUDY OVERSIGHT AND DATA REPORTING / REGULATORY REQUIREMENTS

Adverse event lists, guidelines, and instructions for AE reporting can be found in Section 10 (Adverse Events: List and Reporting Requirements).

13.1 Study Oversight

This protocol is monitored at several levels, as described in this section. The Protocol Principal Investigator is responsible for monitoring the conduct and progress of the clinical trial, including the ongoing review of accrual, patient-specific clinical and laboratory data, and routine and serious adverse events; reporting of expedited adverse events; and accumulation of reported adverse events from other trials testing the same drug(s). The Protocol Principal Investigator and statistician have access to the data at all times through the CTMS web-based reporting portal.

For the Phase 1 portion of this study, all decisions regarding dose escalation/expansion/de-escalation require sign-off by the Protocol Principal Investigator through the CTMS/IWRS. In addition, for the Phase 1 portion, the Protocol Principal Investigator will have at least monthly, or more frequently, conference calls with the Study Investigators and the CTEP Medical Officer(s) to review accrual, progress, and adverse events and unanticipated problems.

All Study Investigators at participating sites who register/enroll patients on a given protocol are responsible for timely submission of data via Medidata Rave and timely reporting of adverse events for that particular study. This includes timely review of data collected on the electronic CRFs submitted via Medidata Rave.

All studies are also reviewed in accordance with the enrolling institution's data safety monitoring plan.

13.2 Data Reporting

Medidata Rave is a clinical data management system being used for data collection for this trial/study. Access to the trial in Rave is controlled through the CTEP-IAM system and role assignments.

Rave role requirements:

- Rave CRA or Rave CRA (Lab Admin) role, must have a minimum of an Associate Plus (AP) registration type,
- Rave Investigator role, must be registered as an Non-Physician Investigator (NPIVR) or Investigator (IVR), and
- Rave Read Only role, site staff must have at a minimum an Associates (A) registration type.

Refer to <https://ctep.cancer.gov/investigatorResources/default.htm> for registration types and documentation required.

If the study has a DTL, individuals requiring write access to Rave must also be assigned the appropriate Rave tasks on the DTL.

Upon initial site registration approval for the study in Regulatory Support System (RSS), all persons with Rave roles assigned on the appropriate roster will be sent a study invitation email from iMedidata. To accept the invitation, site staff must either click on the link in the email or log in to iMedidata via the CTSU members' website under *Data Management > Rave Home* and click to accept the invitation in the Tasks pane located in the upper right-corner of the iMedidata screen. Site staff will not be able to access the study in Rave until all required Medidata and study specific trainings are completed. Trainings will be in the form of electronic learnings (eLearnings) and can be accessed by clicking on the eLearning link in the *Tasks* pane located in the upper right corner of the iMedidata screen. If an eLearning is required for a study and has not yet been taken, the link to the eLearning will appear under the study name in the *Studies* pane located in the center of the iMedidata screen; once the successful completion of the eLearning has been recorded, access to the study in Rave will be granted, and a *Rave EDC* link will replace the eLearning link under the study name.

Site staff that have not previously activated their iMedidata/Rave account at the time of initial site registration approval for the study in RSS will also receive a separate invitation from iMedidata to activate their account. Account activation instructions are located on the CTSU website in the Rave section under the Rave resource materials (Medidata Account Activation and Study Invitation Acceptance). Additional information on iMedidata/Rave is available on the CTSU members' website in the Data Management > Rave section at www.ctsu.org/RAVE/ or by contacting the CTSU Help Desk at [name] or by e-mail at [contact].

